Standard of Care Drugs and Mechanisms	Panitumumab (VECTIBIX) is a recombinant, human IgG2 kappa monoclonal antibody that binds to the human epidermal growth factor receptor (EGFR). Binding of panitumumab to EGFR thus inhibits ligand-induced tyrosine phosphorylation of EGFR. Panitumumab is FDA-approved for the treatment of wild-type KRAS metastatic colorectal cancer (mCRC): In combination with FOLFOX for first-line treatment; and as monotherapy following disease progression after prior treatment with fluoropyrimidine, oxaliplatin, and irinotecan-containing chemotherapy. The site will obtain panitumumab from commercial supply.  Irinotecan (CAMPTOSAR) is a topoisomerase inhibitor. Irinotecan is a derivative of camptothecin. Irinotecan and its active metabolite SN-38 bind to the topoisomerase I-DNA complex, thus inhibiting re-ligation of single-strand breaks induced by topoisomerase intended to relieve torsional strain during DNA replication. Irinotecan is FDA approved, in combination with 5-fluorouracil and leucovorin, for patients with metastatic carcinoma of the colon or rectum; and for patients with metastatic carcinoma of the colon or rectum whose disease has recurred or progressed following initial fluorouracil-based therapy. The site will obtain irinotecan as standard of care from commercial supply.

Treatment Schedule	
Treatment will consist of Cycles lasting 4 weeks (28 days) each.
 
All patients (both phases) are scheduled to receive oral CB-839 twice daily (BID) on a continuous dosing schedule.
 
All patients (both phases) are scheduled to receive panitumumab as a 60 minute (if dose <math>\leq</math> 1000 mg) or 90 minute (if dose <math>></math> 1000 mg) intravenous infusion on Day 1 and Day 15 of each 28 day cycle.
 
All patients in phase I only are scheduled to receive irinotecan as a 90-minute intravenous infusion on Day 1 and Day 15 of each 28 day cycle.
 
On days when both panitumumab and irinotecan drugs are administered (i.e. scheduled for Days 1 and 15 of each cycle), the panitumumab infusion will be completed BEFORE initiation of the irinotecan infusion.

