#### **4.4. Number of Patients and Replacement of Patients Who Discontinue Early**

Approximately 40 patients (about 6-12 in Dose Escalation and up to 29 in Dose Expansion) evaluable for response are anticipated to enroll in this study at Vanderbilt University Medical Center.

In general, it is intended that patients will be treated until confirmed disease progression or intolerable toxicity. The criteria for patient discontinuation are listed in Section 10.

If a patient discontinues study treatment for reasons clearly not related to study treatment, after completing less than 75% of scheduled oral doses of CB-839 and/or less than 2 planned infusions of panitumumab and 2 planned infusions of irinotecan (in phase I) over the first 28 days after initiating protocol-indicated treatment on Cycle 1, Day 1, then that patient will be considered not evaluable for DLT (phase I) or response (phase II) to study treatment and may be replaced with a new patient.

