## **8.6. Discontinuation of Protocol-Indicated Treatment**

All patients will initiate the study via receipt of CB-839 in combination with panitumumab + irinotecan (phase I) or panitumumab only (phase II). Until confirmed disease progression, it is hoped that CB-839 in combination with either panitumumab + irinotecan or only panitumumab will be well tolerated as a combinatorial therapy:

- CB-839 + panitumumab + irinotecan (phase I)
- CB-839 + panitumumab (phase II)

Therefore:

- **A patient must permanently discontinue the study if unable to tolerate CB-839.** (Within the study, a patient will not receive panitumumab + irinotecan as an exclusive 'double-agent' therapy.)
- **Panitumumab and irinotecan treatments are severable; each may be permanently discontinued independently.** (Panitumumab may be discontinued before irinotecan is discontinued, or irinotecan may be discontinued before panitumumab is discontinued.)
- **A patient must permanently discontinue the study if unable to tolerate CB-839 in combination with at least either panitumumab or irinotecan.** (A patient cannot receive just CB-839 as a "single-agent". CB-839 treatment must be received in combination with panitumumab and/or irinotecan: As evaluated within the structure of this study, adequate data supporting the use of CB-839 in the patient population under investigation is not detected.)

The visit schedule for the treatment period will apply until CB-839 treatment in combination with panitumumab ± irinotecan has been permanently discontinued. Once this has occurred, an End-of-Treatment (EOT) visit will be performed within 14 days after the decision of permanent discontinuation, prior to any subsequent anti-cancer therapy.

After the EOT visit, the patient will continue to be followed until 28 days (+7 days) after the last dose of protocol-indicated treatment, at which time the Follow-Up visit must be completed.

Reasons for permanent discontinuation of a patient's protocol-indicated treatment include any of the following:

- Inability to tolerate CB-839 in combination with at least either panitumumab or irinotecan
- Patient withdraws consent to participate
- Occurrence of an AE considered by the investigator to require treatment discontinuation
- Toxicity requiring discontinuation as outlined in Section 10
- Progressive Disease (PD), verified by CT/MRI according to RECIST v1.1

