## **10.7. Guidelines for the Management of Infusion Reactions**

Infusion reactions/hypersensitivity reactions have been reported with panitumumab and irinotecan. An infusion-related reaction is defined as an adverse event occurring during and up to 1 hour after the end of a panitumumab or irinotecan infusion, which is assessed by the investigator to be at least possibly related to the infusion of panitumumab or irinotecan.

Symptoms of an infusion-related reaction may possibly include but are not limited to fever, chills, rigors, diaphoresis, and headache. According to established local procedures, monitor patients during and following an infusion for signs of hypersensitivity and infusion-related reactions with resuscitation equipment readily available.

**Immediately and permanently discontinue respective treatment (i.e. panitumumab or irinotecan for Grade 3 or Grade 4 infusion-related reaction).** For Grade 1 or Grade 2 infusion-related reaction, adjust dose per Table 7 below (in conjunction with any overriding more conservative local policies and procedures for the management of infusion-related reaction).

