### **Reporting period**

Adverse events experienced by participants will be collected and reported from initiation of protocol-indicated treatment for Phase I patients. For Phase II patients, AEs will be collected and reported from the time of the first research scan. AEs will be tracked for all patients in both phases throughout the study through 28 days after the last dose of protocol-indicated treatment. Participants who experience an adverse event related to a study procedure and/or protocol-indicated treatment beyond 28 days will continue to be contacted by a member of the study team until the event is resolved, stabilized, or determined to be irreversible by the participating investigator.

Laboratory and vital sign abnormalities are to be recorded as Adverse Events only if they are medically relevant as judged by the investigator (e.g. symptomatic, requiring corrective treatment, leading to discontinuation and/or fulfilling a seriousness criterion). Unless otherwise specified by protocol or a patient's study physician, abnormal laboratory values of Grade 1 and Grade 2 will be deemed Not Clinically Significant (NCS) and are not required to be individually noted or recorded within the study data.

Baseline disease-related signs and symptoms which are initially recorded as medical history, will subsequently be recorded as adverse events during the trial if they worsen in severity or increase in frequency.

Participants should be instructed to report any serious post-study event(s) that might reasonably be related to participation in this study. The investigator should notify the IRB and any other applicable regulatory agency of any unanticipated death or adverse event occurring after a participant has discontinued or terminated study participation that may reasonably be related to the study.

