## 12.5. Safety Parameters and Definitions

### 12.5.1 Adverse Event (AE)

An adverse event is any undesirable sign, symptom or medical condition or experience that develops or worsens in severity after starting the first dose of study treatment or any procedure specified in the protocol, even if the event is not considered to be related to the study.

Abnormal laboratory values or diagnostic test results constitute adverse events only if they induce clinical signs or symptoms or require treatment or further diagnostic tests.

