Otherwise we will continue accrual up to 29. If 4 or more patients experience BOR among 29 treated, we reject the null hypothesis ( $p < 0.05$ ) of low efficacy (BOR  $\leq 5\%$ ) and declare this regimen sufficiently active in this patient population to warrant further study in more definitive trials. Assuming low efficacy, the probability of early termination is 60% with an expected sample size of 18.

Demographic information such as age, race, and sex, will be tabulated. Descriptive statistics, including means, standard deviations, and ranges for continuous parameters, as well as percentages and frequencies for categorical parameters, will be presented. Adverse medical events will be tabulated. NCI toxicity Grade 3 and Grade 4 laboratory abnormalities will be listed. All patients who received at least one cycle of the combination therapy will be included in the safety analyses.

Power Analysis:

Phase II: We assume a type I error of 5%. If the true RR with this triple agent therapy is 20% or greater, then 29 patients provide 80% power or more to declare this regimen sufficiently active to warrant further study.

Relationship between change in tumor size and radiotracer uptake: We will also evaluate the relationship between radiotracer uptake at baseline and change in tumor size at the time of objective response assessment using a standard linear regression analysis. The slope will describe the shape of the relationship between  $SUV_{max}$  and change in tumor size, while the coefficient of determination ( $R^2$ ) describes the strength of the relationship between the two measures. A similar linear regression analysis will be conducted to quantify the relationship between the change in  $SUV_{max}$  as measured from baseline to after one cycle of therapy and change in tumor size.

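### The safety set requires a cycle to have been received; read strictly, a Phase II patient whom toxicity removes in Cycle 1 counts for response but not in the adverse event tables

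*Combined protocol and SAP*

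**What the plan says.** Section 15 plans tables of adverse events and states one inclusion rule for them: "All patients who received at least one cycle of the combination therapy will be included in the safety analyses". The Synopsis (Treatment Schedule) fixes the length of a cycle: "Treatment will consist of Cycles lasting 4 weeks (28 days) each". No other safety analysis set is named anywhere.

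Collection is wider. Section 12.5.1 counts an event that "develops or worsens in severity after starting the first dose of study treatment or any procedure specified in the protocol", and the Reporting period text in Section 12.1 says "AEs will be tracked for all patients in both phases throughout the study through 28 days after the last dose of protocol-indicated treatment".

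On the response side, Section 4.4 makes a Phase II patient non-evaluable, and replaceable, if the patient "discontinues study treatment for reasons clearly not related to study treatment, after completing less than 75% of scheduled oral doses of CB-839" or falls short on infusions in the first 28 days. The Phase II decision rule in Section 15 uses all patients treated: "If 4 or more patients experience BOR among 29 treated".

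**The concern.** The safety rule ties entry to the tables to how much treatment a patient received, and toxicity is one of the things that cuts treatment short.

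Phase II shows the route. Section 10.7 says of a severe infusion reaction: "Immediately and permanently discontinue respective treatment (i.e. panitumumab or irinotecan for Grade 3 or Grade 4 infusion-related reaction". Section 8.6 adds: "CB-839 treatment must be received in combination with panitumumab and/or irinotecan". Phase II has no irinotecan, so a patient with a Grade 3 or 4 reaction to the first panitumumab infusion must leave in Cycle 1. On the strict reading, the reaction that ended treatment is then absent from the summary of reactions.

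The same patient is not covered by the Section 4.4 exclusion, because the stop was related to treatment. The safety set would therefore be narrower than the response set, in the direction that flatters tolerability.

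The stake is the final adverse event rates, mainly in Phase II, the only part that tests CB-839 with panitumumab alone. Safety is not among the formal Phase II objectives in Section 3.1, but Section 2.5 names it as an aim and Section 15 plans the tables.

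**Working it through.** **1. The plan's own figures.** The inputs from Section 15 are: stop if 0 of 10 respond, reject at 4 or more of 29, null rate 5%, alternative 20%.

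- Early stop under the null: 0.95^10 = 0.599 (plan: 60%).
- Expected sample size: 10 + (1 − 0.599) × 19 = 17.6 (plan: 18).
- Probability of rejecting: the sum over x = 1 to 10 of P(X1 = x) × P(X2 ≥ 4 − x), with X1 binomial on 10 and X2 binomial on 19. This is 0.0468 at 5% and 0.801 at 20% (plan: 5%, and 80% or more).

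The design reproduces. It is not in dispute; it fixes the denominators of 29 and 10 used below.

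**2. Who is in which set (Phase II).**

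| Patient | AEs collected (12.1, 12.5.1) | Response (4.4, 15) | Safety tables, strict reading |
|---|---|---|---|
| Completes Cycle 1 | yes | yes | yes |
| Leaves in Cycle 1, under-dosed, clearly unrelated reason | yes | no, may be replaced | no |
| Leaves in Cycle 1 for toxicity | yes | yes (inferred) | no |

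The third row is the mismatch. It is inferred because no response set is formally named: Section 4.4 does not remove this patient, and Section 15 counts patients treated.

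**3. One fatal Cycle 1 toxicity (Clopper-Pearson 95% intervals).**

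| | Strict reading | Any-dose set |
|---|---|---|
| Full accrual | 0/28 = 0% (0 to 12.3%) | 1/29 = 3.4% (0.1 to 17.8%) |
| Stop after stage 1 | 0/9 = 0% (0 to 33.6%) | 1/10 = 10.0% (0.3 to 44.5%) |

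**4. Other severe events.** The documents give neither the number dropped nor the event rate, so both are assumed. With d of n patients dropped, a 30% rate in those kept and rate r in those dropped, the full rate is ((n − d) × 0.30 + d × r)/n. For d = 1:

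- n = 29: r = 1 gives 9.4/29 = 32.4% (+2.4 points); r = 0 gives 8.4/29 = 29.0% (−1.0).
- n = 10: r = 1 gives 3.7/10 = 37.0% (+7.0 points); r = 0 gives 2.7/10 = 27.0% (−3.0).

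If instead k patients leave with the event and 3 others have it (also assumed), the strict reading gives 3/(29 − k) and the any-dose set (3 + k)/29: 10.7% against 13.8% for k = 1, 11.1% against 17.2% for k = 2, and 11.5% against 20.7% for k = 3.

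**5. How often it could arise.** No Cycle 1 toxicity exit rate is given for this combination. With an assumed rate q, the chance of losing at least one of 29 is 1 − (1 − q)^29: 44%, 77% and 95% for q = 2%, 5% and 10%. For the first 10 patients it is 18%, 40% and 65%.

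Deaths from any cause also remove patients from the strict set. Section 15 assumes exponential survival with a median of 6.4 months. Taking 28 days as 0.92 months, 1 − 2^(−0.92/6.4) = 9.5%, or about 2.7 of 29. Most would be disease deaths, and entry restricted to ECOG 0 or 1 may lower the figure. The events of such patients still count, since Section 12.5.1 does not require relatedness.

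**The case against.** The strongest answer is that this is loose wording and not a demonstrated exclusion. The sentence says who is included and does not say that nobody else is. The statement in the same paragraph that adverse events will be tabulated carries no restriction. Infusions fall only on Days 1 and 15, so a patient dosed through Day 15 might already be held to have received a cycle. This stands in part: the looser reading is possible. But the protocol schedules its scans after one cycle for Days 22 to 28 or pre-dose on Day 29 (Section 6.1, note 13), and it refers to the first dose when it means the start of treatment (Sections 4.2 and 12.5.1). The strict reading is therefore the natural one. Section 12 governs what is collected, not who is analysed.

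Second, the response side is inferred. A patient who dies in Cycle 1 would normally have no scan after baseline, because re-scanning is every 8 weeks, and the plan does not say how that patient is classified. That caveat stands, though nothing in the text contradicts the inference.

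Third, few patients may be affected. Section 2.4.2 reports that 6 of 147 patients (4.1%) stopped CB-839 for adverse events. That is monotherapy over all treatment time, so it is neither a Cycle 1 rate nor a rate for the combination. Most toxicity here also leads to holds and not exits (Sections 10.2 and 10.3).

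Fourth, a fatal event could not go unseen. Deaths and serious events are reported under Sections 12.7.3 and 12.7.9, and the monitoring committee reviews all serious events quarterly (Section 13.3). This stands and limits the harm to the summary tables.

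**Conclusion.** The concern holds as stated. The only safety-set rule in the plan, read strictly, omits treated patients who leave in Cycle 1. In Phase II that includes patients removed by toxicity who still count for response.

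The conclusion rests on the strict reading and, for the response half, on reading Sections 4.4 and 15 together. The clearest effect is whether an event appears at all: 0/28 against 1/29, or 0/9 against 1/10, with overlapping intervals. For other events, the size and even the direction depend on assumed numbers.

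The reach is limited. Phase I DLT counting and MTD selection follow their own rules in Sections 4.4 and 10.1, a related fatal Cycle 1 toxicity in Phase I is a Grade 5 DLT, and no hypothesis test uses this set. It should be fixed, but it does not threaten the design.

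**What to change.** Replace the sentence in Section 15 with: *All patients who receive any dose of CB-839, panitumumab or irinotecan, including patients later replaced, will be included in the safety analyses.* Keep the DLT-evaluable and replacement rules of Sections 4.4 and 10.1 unchanged, as a separate set.

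Two additions would help but are not essential. Phase II events are collected from the first research scan, so events in patients scanned but never dosed could be listed separately. Naming the response set, and saying how a patient without a scan after baseline is counted, would settle the inference above.

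The cost is one sentence, with no new data, no change to the two-stage design and no change to patient management. Adverse event rates may look slightly less favourable, and the safety denominator may exceed 12 in Phase I or 29 in Phase II because replaced patients stay in it. If an any-dose set was always meant, the change only records that.

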All patients in Phase II will undergo two  $^{18}F$ -FSPG imaging sessions at baseline and just prior to cycle 2 of therapy. Our preliminary data suggest that the  $^{18}F$ -FSPG  $SUV_{max}$  (predictor) has a standard deviation of 2.04 (95% CI 1.42 to 3.58). From previous clinical trial data, the median (range) and mean (standard deviation) of the change in the sum of index lesions from patients treated with EGFR mAb therapy were 4.9 mm (-24 mm to 42 mm) and 6 mm (15.8 mm), respectively. Using the standard deviations (SDs) and their 95% confidence intervals for PET  $SUV_{max}$  (predictor) and change in tumor size, table 11 lists the true slope estimates that provide 80% power to reject the null hypothesis of no association between  $^{18}F$ -FSPG imaging and tumor response. From the estimated SDs for PET  $SUV_{max}$  and change in tumor size, a reformulation of the coefficient of determination ( $R^2$ ) gives the correlation associated with the slope estimates

$$r = \sqrt{\frac{1}{(\sigma/B \cdot SX)^2 + 1}}$$

where  $\sigma$  is the SD of the residuals,  $B$  is the slope and  $SX$  is the standard deviation for PET  $SUV_{max}$ .

The estimated correlations for the scenarios in table 11 have a mean ( $\pm$  standard deviation) of  $0.475 \pm 0.0002$ , which represent biologically and clinically meaningful associations between early changes in PET  $SUV_{max}$  and tumor size.

Because  $^{11}C$ -Glutamine is a novel tracer, we will use the same power and sample size analyses as  $^{18}F$ -FSPG.

Table 12. True slope estimates required to achieve 80% power to reject the null hypothesis of no association between baseline PET  $SUV_{max}$  and change in the sum of index lesions.

SD for $^{18}F$ -FSPG $SUV_{max}$	SD for Change in Tumor Size at Best Response		
	12	16	24
1.42	4.01	5.35	8.03
2	2.85	3.80	5.70

[figure not shown]
3.58	1.59	2.12	3.18
------	------	------	------

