A similar linear regression will be conducted to predict change in tumor size by the change in PET  $SUV_{max}$  measured just prior to cycle 2. Using a standard deviation of 2 from table 11, we can estimate the SD of the difference in PET  $SUV_{max}$  as  $\sqrt{2V(1-r)}$  where  $V$  is the assumed common variance (for a single SD of 2, the  $V=4$ ) of the two measurements and  $r$  is the correlation between them. For a correlation set of 0.3, 0.5, and 0.7, the SD's of the difference in PET  $SUV_{max}$  are 2.36, 2, and 1.54. The data in table 12 reflect an average (SD) correlation between change in tumor size and  $\Delta SUV_{max}$  of  $0.475 \pm 0.0003$ .

Table 13. True slope estimates required to achieve 80% power to reject the null hypothesis of no association between change in PET $SUV_{max}$ just prior to cycle 2 and change in the sum of index lesions.			
SD for $^{18}F$ -FSPG $SUV_{max}$	SD for Change in Tumor Size at Best Response		
	12	16	24
1.54	3.70	4.93	7.4
2	2.85	3.80	5.70
2.37	2.40	3.21	4.81

Time-to-event. We expect median progression-free and overall survival of approximately 1.9 and 6.4 months, respectively. Power to reject a  $HR=1$  for a single predictor in the Cox regression model depends on the number of events (progressions or deaths), the variability of the predictor, and the true HR [14]. Assuming exponential survival, we estimate that 29 and 21 patients will have progressed or expired by 12 months among the 29 patients in the phase I/II trial. We will use Cox proportional hazards model to estimate the association between PET  $SUV_{max}$  and PFS and OS. Preliminary data suggest  $^{18}F$ -FSPG  $SUV_{max}$  has a standard deviation of 2.04 (95% CI 1.42 to 3.58). Figure 4 illustrates the hazard ratios necessary to reject the null hypothesis that  $HR=1$  versus the alternative that the  $HR \neq 1$  assuming SD estimates for PET  $SUV_{max}$ , a type I error of 5% and 80% or 90% power. For PFS and OS, we expect to have at least 90% power to reject the null hypothesis that the  $HR=1$  if the for a SD PET  $SUV_{max}$  of 1.54 and the true hazard ratios are 1.65 and 1.53 or larger, respectively.

**Figure 5:** True hazard ratios (HRs) scenarios necessary to reject ( $p<0.05$ ) a null hypothesis with 80% and 90% power.

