### Power Analysis:

PFS/OS. Estimated median PFS and OS in this patient population is 1.9 and 6.4 months, respectively, with an estimated 29 and 21 patients progressing or expired by 12 months. In preliminary data, the average standard deviation (SD) and bootstrapped (1000 replications) 95% confidence intervals of the SD for the deltaCt values of 84 genes was 2 cycles (1.85 to 2.14 cycles). Twenty-nine patients provide at least 90% power to reject the null hypothesis that the HR=1, assuming the qRT-PCR SD is 2 for true hazard ratios are 1.35 and 1.42 or larger, respectively.

**Figure 6:** True hazard ratios (HRs) scenarios necessary to reject ( $p<0.05$ ) a null hypothesis with 80% and 90% power.

Change in Tumor Size. Among 20 patients treated with mAb therapy, the mean SD of the change in the sum of index lesions was 6 mm (15.8 mm). Using the SD and their 95% confidence intervals for qRT-PCR (predictor; data provided above) and change in tumor size among 29 patients, table 2 lists the true slope estimates that provide 80% power to reject the null hypothesis of no association between qRT-PCR and tumor response. Given our preliminary data, 29 patients provide 80% power to detect ( $p<0.05$ ) a 3.8 mm change in tumor volume per deltaCt cycle.

Table 14. True slope estimates (mm/cycle) required to achieve 80% power to reject the null hypothesis of no association between baseline qRT-PCR and change in the sum of index lesions.

SD for qRT-PCR	SD for Change in Tumor Size at Best Response		
	12	16	24
1.85	3.08	4.11	6.16

2	2.85	3.80	5.70
2.14	2.66	3.55	5.33

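### The planned change-in-SUVmax regression cannot separate early change in uptake from baseline uptake, and neither tumour-change regression adjusts for baseline tumour size

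*Combined protocol and SAP*

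**What the plan says.** Section 15 (Statistical Considerations) evaluates baseline SUVmax against change in tumour size "using a standard linear regression analysis". For the second predictor it says "A similar linear regression analysis will be conducted to quantify the relationship between the change in" SUVmax from baseline to after one cycle and tumour change, and later repeats: "A similar linear regression will be conducted to predict change in tumor size by the change in PET" SUVmax measured just before cycle 2.

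Everything that follows is for one predictor. R2 "describes the strength of the relationship between the two measures", the correlation formula contains one slope and one predictor SD, and the table captioned 12 "lists the true slope estimates that provide 80% power to reject the null hypothesis of no association between" imaging and tumour response. The table captioned 13 does the same for change in SUVmax. The outcome is absolute change in millimetres. No covariate is named for either regression.

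Both candidate covariates are already collected. Pre-treatment SUVmax is part of a Phase II secondary endpoint (Section 3.2). Baseline tumour burden comes from the baseline CT or MRI (Section 7.10) and is needed for RECIST (Appendix 3), and Phase II patients must have a measurable lesion (Section 4.1).

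**The concern.** A change score contains the baseline value with a negative sign, so change in SUVmax is tied to baseline SUVmax by construction. The plan's first regression is powered on the idea that baseline SUVmax itself relates to tumour change. If that idea is right, the second regression inherits part of the same relationship even when the second scan carries no further information.

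This matters because Section 2.6.1 hopes the paired scans will give a pharmacodynamic measure of CB-839 activity over time. Suppose high baseline uptake goes with more shrinkage, as the rationale in Sections 2.6.1 and 2.6.3 would suggest. The coupling then makes a larger fall in SUVmax accompany more shrinkage, which is the pattern a drug effect on uptake would show.

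Separately, change in millimetres may depend on how large the tumour was at the start. Leaving baseline size out can cost precision, or allow confounding if uptake also depends on size.

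**Working it through.** **Inputs from Section 15.** SD of SUVmax 2 (common variance V = 4); SD of tumour change 16 mm; correlation between the two scans r = 0.3, 0.5, 0.7; design correlation 0.475; power 80%. The Phase II power paragraph gives 5% type I error. The sample size of 29 is stated for the parallel qRT-PCR slope table ("change in tumor size among 29 patients"), whose SD = 2 row is identical. Sidedness is not stated; a two-sided test reproduces the tables.

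**1. The plan's own figure.** Correlation = slope × SD(SUVmax) / SD(tumour change) = 3.80 × 2 / 16 = 0.475. The noncentrality is √29 × 0.475 / √(1 − 0.475²) = 2.907. On 27 degrees of freedom the power is 0.80. A correlation of 0.4749 returns all nine slopes of Table 12. (This reads 12, 16 and 24 mm as total SDs.)

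**2. Coupling of change with baseline.** Let D = scan 2 − scan 1. The plan gives Var(D) = 2V(1 − r). Also Cov(D, scan 1) = rV − V = −V(1 − r). Hence corr(D, baseline) = −√((1 − r)/2).

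**3. Rejection when the second scan adds nothing.** If baseline SUVmax correlates 0.475 with tumour change, and D is unrelated to tumour change given baseline, the correlation of D with tumour change has size 0.475 × √((1 − r)/2). The noncentral-t calculation (n = 29) was checked by multivariate-normal simulation (40,000 runs).

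| r between scans | corr(D, baseline) | Size of implied corr(D, tumour change) | Unadjusted rejection, noncentral t | Unadjusted, simulated | Baseline SUVmax included, simulated |
|---|---|---|---|---|---|
| 0.3 | −0.59 | 0.28 | 33% | 32% | 5% |
| 0.5 | −0.50 | 0.24 | 25% | 24% | 5% |
| 0.7 | −0.39 | 0.18 | 16% | 16% | 5% |

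If baseline SUVmax correlates only 0.3 with tumour change, simulated unadjusted rejection is 15%, 13% and 9%. If it correlates 0, the rate is 5%.

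**4. Price of including baseline SUVmax.** The slope variance is inflated by 1/(1 − (1 − r)/2) = 2/(1 + r). Take a true effect of D at 0.475 and no effect of baseline SUVmax of its own, with 26 degrees of freedom:

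| r | Variance inflation | Noncentrality | Power | Partial correlation of baseline SUVmax with tumour change needed to regain 80% |
|---|---|---|---|---|
| 0.3 | 1.54 | 2.907/√1.54 = 2.34 | 0.62 | 0.59 |
| 0.5 | 1.33 | 2.907/√1.33 = 2.52 | 0.68 | 0.50 |
| 0.7 | 1.18 | 2.907/√1.18 = 2.68 | 0.73 | 0.39 |

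Simulation with random predictors gives somewhat lower values throughout: 0.76 unadjusted, and 0.57, 0.63 and 0.69 adjusted.

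**5. Baseline tumour size.** The documents give no correlation of size with SUVmax or with tumour change, so these are illustrations over assumed ranges.

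- *Size independent of SUVmax.* Power is 2.907/√(1 − partial r²) referred to 26 degrees of freedom. It is 0.80, 0.81, 0.83, 0.86 and 0.90 for partial correlations of 0, 0.2, 0.3, 0.4 and 0.5 between size and tumour change.
- *Size related to both, SUVmax with no effect given size.* Unadjusted rejection in the baseline model is 5% if either correlation is 0, 7% at 0.3 and 0.3, and 26% at 0.5 and 0.5. Adjusted, it is 5% throughout.
- *Size related to SUVmax but not to tumour change.* Adjustment costs power: simulated 0.76 falls to 0.71 at a correlation of 0.3, and to 0.63 at 0.5.

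**The case against.** The strongest reply is that the plan sets out to quantify a relationship between two measures, and the one-predictor slope estimates that marginal association validly. Its stated null is no association between change in SUVmax and change in the sum of lesions. In the scenario of step 3 such an association exists (0.28, 0.24 or 0.18 in size), so rejecting is correct. A reader might infer that 16% to 32% is the type I error of the planned test; it is not. It becomes an error only under a different null: no association beyond baseline. This part of the reply stands in full.

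A reader might also infer that leaving the covariates out necessarily loses power. The calculations do not support that. Including baseline SUVmax lowers power unless it is itself strongly related to tumour change, and the gain from tumour size depends on correlations that the documents do not give. The precision gain in step 5 assumes size and SUVmax are independent, while the confounding assumes they are not, so the two benefits cannot simply be added.

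Third, adjustment changes the question. With baseline SUVmax in the model, the coefficient on change equals the coefficient on the second scan, so the test asks whether scan 2 adds to scan 1. Making that the sole main result would be a choice of estimand, not a correction.

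Finally, these are secondary correlative analyses in up to 29 patients and do not touch the response-rate decision. A one-predictor model is defensible at that size. What the reply does not answer is how a significant unadjusted change slope could be read as evidence about the second scan.

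**Conclusion.** The point holds as a limit on interpretation. The coupling of −0.39 to −0.59 follows from the plan's own formula and scan correlations. The rejection rates of about 32%, 24% and 16% rest on two further assumptions: that baseline SUVmax has the 0.475 correlation for which the first regression is powered, and that the second scan adds nothing. With no link between baseline SUVmax and tumour change the rate is 5%. The planned change model is therefore valid for the marginal association, but it cannot by itself support a pharmacodynamic claim.

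For baseline tumour size, omission can cost precision or allow confounding, by an amount the documents do not allow one to fix.

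A reader might conclude that the planned regressions are invalid and must be replaced. The documents do not support that either: the unadjusted slope answers the question as written, and the adjusted one answers another at a real cost in power. The 80% power of Table 13 belongs only to the unadjusted slope.

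**What to change.** In Section 15:

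- Include the baseline sum of target-lesion diameters as a covariate in both tumour-change regressions.
- Pre-specify a change-in-SUVmax model that also contains baseline SUVmax, and report its slope and partial R2 beside the planned unadjusted model.
- State that any claim that early change in uptake adds information will rest on the slope adjusted for baseline SUVmax.
- State that Table 13's 80% power applies to the unadjusted slope, and that power for the slope adjusted for baseline SUVmax is about 0.62 to 0.73 when baseline SUVmax has no effect of its own.

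This needs wording and a power note, but no new data, visits or patients. The statistical cost is one or two of 27 residual degrees of freedom, a possible loss of power if tumour size correlates with SUVmax, and the lower power just stated. Settling it before analysis also avoids choosing covariates after the results are seen.
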